8.2 External datasets

8.2.1 Intervention delivery

Data on the delivery of the intervention will be collected via Qualtrics and the Change One Thing app:

- Session duration;
- Number of sessions delivered;
- Mode of delivery (remote, phone, in person): frequencies/percentages;
- List of content areas with number of participants who discussed each content area;
- Duration a participant stayed with the same action plan/content area;
- Number of content areas covered during total intervention period and workbook and/or Change One Thing app.

9 Sample Size

Original sample size calculation

The sample size calculation was based on detecting a clinically meaningful difference of 5.5 mmol/mol (0.5%) in HbA1c at 12 months. This difference was selected based on data from trials of diabetes self-management in the general diabetes population and NICE guideline on type 2 diabetes management. Based on the variation observed in HbA1c in a Clinical Practice Research Datalink (CPRD) population study, we assumed a standard deviation of 15.3 mmol/mol. Based on attrition rates in previous severe mental illness trials, we expect approximately 20% attrition. In the intervention arm, a DIAMONDS Coach will deliver the intervention to multiple participants, and therefore the outcomes of participants with the same coach may be correlated. Although only a small clustering effect is expected, this provides a more conservative sample size estimate. The sample size was therefore adjusted for clustering in the intervention arm.

For approximately 90% power, at the 5% significance level, assuming an average cluster size of 10-12 participants per DIAMONDS coach with an intraclass correlation (ICC) of 0.02 in the intervention

DIAMONDS Statistical Analysis Plan version 1 Page | 10 arm, and adjusting for 20% attrition, we estimate we will need to randomise 450 participants, with 225 per treatment group.

Revised sample size calculation

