In February 2024 following discussion with the TSC, an amendment was made to the original sample size calculation described above due to slower than anticipated recruitment. We amended the sample size by including an adjustment for the correlation between baseline and 12-month HbA1c (0.3) to reflect the repeated measures analysis model planned for the primary analysis. This led to a minimum sample size of 380 participants needed; keeping all other assumptions the same would achieve 88% power. However, we will continue recruiting beyond this minimum target until the end of the agreed recruitment window.

10 Randomisation and blinding

As stated in the protocol:

Consenting participants will be randomised on a 1:1 allocation ratio to either the DIAMONDS intervention or the usual care group using computer generated permuted blocks of random sizes. Randomisation will be carried out by York Trials Unit (YTU) independently of the R&D team using a secure, online randomisation service to ensure allocation concealment.

The DIAMONDS Programme Manager and Trial Coordinators will be unblinded to allocation in order to facilitate contact between randomised participants and their designated DIAMONDS Coach, if required. Following randomisation, the participating site will contact DIAMONDS Coaches to advise them to approach participants randomised to the intervention group to arrange the first intervention session.

Statisticians will not remain blind during the study but will not see any unblinded primary outcome data until a version 1 of the statistical analysis plan has been signed off.

11 Analysis of internal pilot trial/phase

As stated in the protocol:

Recruitment rate and the 95% confidence interval will be estimated from the pilot data collected. A CONSORT diagram will produced with the following outcomes: number of eligible participants; proportion of eligible participants approached for consent; proportion of eligible participants not approached and reasons why; proportion of participants approached who provide consent; proportion of participants approached who do not provide consent; proportion of participants providing consent who are randomised; proportion of participants randomised who do not receive the randomly allocated treatment; proportion of participants dropping out between randomisation and follow-up.

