12.2 Analysis principles and populations

Analysis of primary and secondary outcomes will be intention-to-treat (ITT) (unless otherwise stated) and tests will be two sided at 5% significance level.

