12.6 Primary analysis

The primary outcome (HbA1c at 12-month post-randomisation) will be analysed using a partiallynested mixed effects regression model, with HbA1c scores at 6- and 12-months follow-up as the dependent variable, adjusting for baseline HbA1c scores and outcome source (central lab or medical records), randomised treatment group, time and a treatment group-by-time interaction will be included as fixed effects and participant and DIAMONDS coach as a random effect nested within treatment arm (9). Different covariance patterns for the repeated measurements will be explored and the most appropriate pattern will be used for the final model. Diagnostics including Akaike's information criterion will be compared for each model (smaller values are preferred). The model assumptions (normality of residuals, homoskedasticity and multicollinearity) will be evaluated using residual plots and calculating variance inflation factors (VIFs).

The estimated treatment group difference at 12 months will be reported as the primary endpoint with the associated 95% confidence interval and p-value (Ref: Table 7). Analysis of the primary outcome will be checked by a second statistician. The analysis model does not match exactly the method used in the sample size calculation which simply compares one follow up point (12 months) with an adjustment for baseline correlation. This is a more conservative approach so we should still have adequate power for the primary analysis.

HbA1c is being collected from different sources:

Central laboratory- participant must consent to bloods being taken at their visit. The sample is then sent to a central laboratory in Manchester. Blood results are returned to YTU and recorded on a Bloods CRF by YTU staff.

Medical records- if lab results are unavailable (e.g. participant refuses to have blood samples taken), the investigator may use medical records to look up a recent blood test result and corresponding date which will be recorded on that CRF (baseline, Month 6 or Month 12).

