12.9 Analysis of secondary outcomes

BMI, smoked at any point in the last 7 days (yes or no), BPRS scores, PHQ-9 scores and PAID-5 scale scores will be analysed using mixed effects regression analysis for continuous outcomes, and logistic mixed models for binary outcomes. Baseline scores, randomised treatment group, time and a treatment group-by-time interaction, sex and age will be included as fixed effects and participant and DIAMONDS coach as random effects (to reflect the primary analysis model). Models will include assessments at all available time-points and will provide an overall treatment effect over 12 months, as well as estimates at individual time-points (6 and 12 months), reported as estimates and 95% confidence intervals. Different covariance patterns for the repeated measurements will be explored, and the most appropriate pattern will be used for the final model.

Other secondary outcomes (total cholesterol, HDL cholesterol, triglycerides, LDL cholesterol, haemoglobin, systolic BP, diastolic BP, waist circumference, urinary albumin: creatinine ratio, insulin use, diabetes complications, EQ5D-5L scores, IPAQ levels and SDSCA category scores) will be presented descriptively by treatment arm.

Accelerometer data will be collected at baseline and 6-months post-randomisation. Data will be analysed using the R-package GGIR, which performs signal processing of the raw data, including auto-calibration, detection of abnormal values, detection of non-wear, and calculation of the average magnitude of dynamic acceleration (Euclidean norm minus one g [ENMO]). Files will then be exported to Stata or similar statistical software for further analysis. Descriptive statistics will be reported by treatment group at each time point (baseline and 6 months) and differences between treatment groups will be reported, adjusted for baseline.

Based in findings from the feasibility study, analysis will be restricted to participants who had at least 4 valid days of accelerometer monitoring (out of a planned 7 days). The following summaries will be presented by treatment arm for all days and split by weekdays and weekend days:

- Number of valid days the participants wore the accelerometer (n (%), mean (SD);
- Valid wear time in hours (mean and SD);
- Number and percentage of participants with the required number of valid days;
- Time spent engaging in light activity (minutes per day) (mean and SD);

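### The primary model has a coach effect in the intervention arm but no site effect shared by both arms, which can widen the confidence interval and cost power if sites differ in HbA1c

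*SAP*

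**What the plan says.** Section 4 describes a multi-centre, individually randomised trial. Section 10 describes 1:1 allocation in permuted blocks and names no stratification factor. It says that after randomisation "the participating site will contact DIAMONDS Coaches to advise them to approach participants randomised to the intervention group".

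The primary model in section 12.6 has fixed effects for baseline HbA1c, outcome source, arm, time and arm-by-time, and "participant and DIAMONDS coach as a random effect nested within treatment arm". Site, age and sex do not appear.

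Section 12.9 gives the secondary models the same core terms and adds two covariates: "sex and age will be included as fixed effects and participant and DIAMONDS coach as random effects (to reflect the primary analysis model").

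The sample size in section 9 allows for clustering in the intervention arm only, "assuming an average cluster size of 10-12 participants per DIAMONDS coach with an intraclass correlation (ICC) of 0.02 in the intervention" arm. The revised minimum of 380 participants, with a baseline correlation of 0.3, is said to give 88% power. Recruitment is to continue beyond that minimum while the window is open.

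**The concern.** Both arms are recruited at the same sites. A difference in HbA1c level between sites therefore affects intervention and control participants alike and largely cancels in the treatment contrast. The model in 12.6 cannot represent this, because its only cluster-level variance is the coach variance in the intervention arm. If a coach's caseload comes mostly from one site, the coach variance absorbs the site differences. The model then counts as noise something that has largely cancelled.

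At stake are the width of the primary confidence interval and part of the planned power, in a trial whose target was reduced because recruitment was slow.

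The covariates raise a separate question. Section 12.9 invokes the primary model while adjusting for age and sex, which the primary model does not contain. This plays no part in the coach mechanism.

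**Working it through.** **Inputs.** Section 12.2: "tests will be two sided at 5% significance level". Section 9: "detecting a clinically meaningful difference of 5.5 mmol/mol (0.5%) in HbA1c at 12 months"; "we assumed a standard deviation of 15.3 mmol/mol"; "we expect approximately 20% attrition"; 10-12 participants per coach, ICC 0.02; baseline correlation 0.3; N = 380 (before revision, 450). Site ICCs are not in the SAP. They are assumed here and shown as a range.

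**Step 1: reproduce the stated power.** SE = SD × √((DE + 1)/n), with DE = 1 + (m − 1) × 0.02 in the intervention arm only.

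- Before revision: n = 450 × 0.8/2 = 180 per arm, m = 11, DE = 1.20. SE = 15.3 × √(2.20/180) = 1.69, power 90.2% (90.4% to 89.9% for m = 10 to 12). Stated: about 90%.
- Revised: n = 380 × 0.8/2 = 152, SD = 15.3 × √(1 − 0.3²) = 14.60. SE = 14.60 × √(2.20/152) = 1.756, power 87.9% (88.2% to 87.7%). Stated: 88%.

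Both reproduce.

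**Step 2: how site variance enters the standard error.** Take J = 15 sites, one coach each, and m = 10 per arm per site (300 analysed). The residual variance is 15.3² × 0.91 = 213.0 and the coach ICC is 0.02, so the coach variance is 4.26. At an assumed site ICC of 0.05 the site variance is 10.65. The remaining variance is 0.93 × 213.0 = 198.1 in the intervention arm and 0.95 × 213.0 = 202.4 in control.

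- True variance of the contrast (site cancels): 4.26/15 + (198.1 + 202.4)/150 = 2.954, SE 1.72.
- Variance the model without site reports: (10.65 + 4.26)/15 + 198.1/150 + 213.0/150 = 3.735, SE 1.93.

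Power is then about Φ((5.5 − 1.96 × 1.93)/1.72) = Φ(1.00), or 84%. The same steps at 0.10 give SEs of 1.68 (true) and 2.09 (reported).

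Adding the site ICC to the design effect in the Step 1 formula gives 80.7% at 0.05. That overstates the loss, because it treats the inflated SE as the true one.

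**Step 3: simulation.** 12-month outcome only, 15 sites, one coach each, coach ICC 0.02, effect 5.5. The first set is balanced, with moment estimators (300 analysed, 20,000 runs). The second uses REML with unstratified allocation (304 analysed, 2,400 runs; Monte Carlo error about 0.7 points).

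| Assumed site ICC | Power without / with site, balanced | Power without / with site, REML | Type I error without site, balanced / REML |
|---|---|---|---|
| 0 | 87.5% / 85.9% | 86.7% / 87.3% | 4.6% / 4.6% |
| 0.01 | 86.2% / 85.4% | not run | 4.7% / not run |
| 0.02 | 85.8% / 86.0% | 85.5% / 87.4% | 4.3% / 4.5% |
| 0.05 | 83.3% / 87.0% | 83.4% / 87.6% | 3.2% / 3.4% |
| 0.10 | 78.8% / 88.4% | 78.7% / 88.3% | 2.1% / 2.3% |

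Two further REML runs of this layout gave 83% against 87% and 85% against 89% at 0.05. At 0.10 they gave 80% against 88% and 80% against 89%. With a REML site intercept, type I error stayed between 4.6% and 5.2%.

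**Step 4: is one coach per site plausible?** At 11 per coach, 152 analysed in the intervention arm imply about 14 coaches, and 190 randomised about 17. Section 11 sets 15 sites as the green target for the pilot. The numbers are compatible with one coach per site but do not establish it.

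**Step 5: age and sex.** Section 12.6 lists neither and section 12.9 lists both. The SAP does not say how much HbA1c variance they explain, so no precision gain can be calculated.

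**The case against.** The strongest reply is that the loss depends on two facts the SAP does not state: an appreciable site ICC after baseline adjustment, and coaches tied to single sites. This stands.

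- The 15 sites are a pilot threshold, not the trial's site count. Sessions can be held remotely or by phone, so a coach may cover several sites.
- In a balanced approximation with each coach covering two sites, power without a site term is about 86% at a site ICC of 0.05 and 85% at 0.10, against 87% with no site variance.
- If the 0.02 was meant to cover coach and site together, nothing is lost against plan.
- The 6-month data and recruitment beyond 380 may offset the loss. With 360 analysed (450 × 0.8), power without a site term stays near 90% at 0.05, even with one coach per site.
- Use of one central laboratory, with adjustment for outcome source, limits site differences due to measurement.

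A second reply is that a site term has a cost. The balanced simulation shows 1.6 points at site ICC 0, but it uses simple moment estimators. REML, the more relevant fit, shows no visible cost there (86.7% without site, 87.3% with; in a further run 88.2% and 88.5%). This reply does not stand against a random intercept fitted by REML.

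On age and sex, the parenthesis in 12.9 directly follows the random effects and may describe only those, which do match 12.6. A reader might infer a proven contradiction. The text supports only an unexplained difference between the covariate sets.

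**Conclusion.** The point holds as a conditional improvement to the primary model. Without a site effect common to both arms, section 12.6 can overstate the standard error when coaches sit within sites and sites differ. For 15 sites, one coach each and about 300 analysed at 12 months, the power given up is about 0-2 points at an assumed site ICC up to 0.02, about 4 points at 0.05 and 8-10 points at 0.10. It is smaller if coaches span sites.

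Two stronger readings are not supported. A reader might infer that the 88% is wrong or has already been eroded. It reproduces from its own inputs, and the SAP supplies neither a site ICC nor a coach-to-site map from which to show a loss. A reader might also infer that the primary result would be biased or falsely positive. The error runs the other way: the estimate is not biased and the test is conservative.

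The difference in age and sex between 12.6 and 12.9 is a separate matter of consistency. Its effect on precision cannot be sized from the SAP.

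**What to change.** In section 12.6, add a random intercept for site common to both arms and keep the coach random effect in the intervention arm. State that the site term will be dropped if its variance is estimated at zero. The sample size statement in section 9 needs no change.

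As a separate edit, add baseline age and sex to the fixed effects in 12.6 so that the primary and secondary models match.

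The cost is SAP wording and one more variance component to estimate. No new data are needed: section 12.3 already reports recruitment by site, and section 12.7.2 already uses age and sex for imputation.

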7.1 Primary outcome(s)

The primary outcome of the main trial is glycated haemoglobin (HbA1c) at 12 months postrandomisation. It will also be measured at 6 months post randomisation as a secondary outcome. Participants who do not want a blood test can consent to their most recent routine blood test results being used if that test was taken between 6 weeks before and 6 weeks after the follow up date. This measure is collected in the bloods case report form (CRF).

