DIAMONDS Statistical Analysis Plan version 1 Page | 13 The primary analysis will include all HbA1c values from both sources providing they are within +/-6 weeks from the date of the specified timepoint (baseline, 6- and 12-months post randomisation). Values outside of this window will be counted as missing. We will conduct analyses with all observed data. Mixed effects regression models use all available data and assume missing outcome data are missing at random. To explore this assumption, we will summarise the baseline characteristics of participants with and without missing outcome data and further sensitivity analyses are outlined in section 12.7.

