12.8 Subgroup analyses

Subgroup analyses will be performed to explore the potential effect of the following subgroups:

- Participants with good and those with suboptimal diabetes control at baseline as defined as High control (HbA1c values <= 58 mmol/mol) and Low control (HbA1c values >58 mmol/mol)
- Ethnicity (White, Asian or Asian British, Black, Black British, Caribbean or African, Mixed or multiple ethnic groups or Other Ethnic background)
- Insulin use status (Prescribed insulin Yes or No)
- Urdu speakers (Yes or No)

DIAMONDS Statistical Analysis Plan version 1

As we are unable to predetermine the numbers in each subgroup, the completion of each subgroup analysis will be subject to there being sufficient numbers in the group.

The primary analysis model will be refitted with an interaction term between the randomisation group and the specified subgroup variable. Treatment effect for these subgroups will be reported as adjusted mean differences with their associated 95% CI and p-values (Ref: Table 8). As recommended by the literature, the subgroup analysis will be restricted to the primary analysis

and subgroups will be defined by baseline data i.e. data that is not dependent on the intervention(14). Subgroup analysis will be performed regardless of the results of the primary analysis.

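### The ±6-week HbA1c window also covers baseline, so a value dated after randomisation can serve as the baseline covariate and as the 58 mmol/mol subgroup variable

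*SAP*

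**What the plan says.** Section 12.6 (Primary analysis) decides which HbA1c values enter the analysis. Values from the central laboratory and from medical records both count, "providing they are within +/-6 weeks from the date of the specified timepoint (baseline, 6- and 12-months post randomisation"; anything outside that window is set to missing. Baseline is named alongside the two follow-up points, with the same two-sided window.

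Section 7.1 (Primary outcome) is narrower. A routine result may be used "if that test was taken between 6 weeks before and 6 weeks after the follow up date", and baseline is not mentioned.

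For the medical-record route, section 12.6 says that when laboratory results are unavailable "the investigator may use medical records to look up a recent blood test result and corresponding date", to be entered on the baseline, month 6 or month 12 form.

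Baseline HbA1c is used twice:
- The primary model is specified as "adjusting for baseline HbA1c scores and outcome source (central lab or medical records").
- Section 12.8 (Subgroup analyses) splits participants into "High control (HbA1c values <= 58 mmol/mol) and Low control (HbA1c values >58 mmol/mol"), and states that "subgroups will be defined by baseline data i.e. data that is not dependent on the intervention".

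On timing, section 10 (Randomisation and blinding) says: "Following randomisation, the participating site will contact DIAMONDS Coaches to advise them to approach participants randomised to the intervention group". It gives no minimum delay before the first session. Section 12.5 lets coach and participant meet as often as they wish over six months.

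**The concern.** A symmetric window is natural around a follow-up date. Around baseline it is not, because the later side can cross randomisation. An intervention-arm value drawn after coaching has started may already carry part of the treatment effect. Adjusting for it removes that part from the estimated 12-month difference, and a larger sample does not cure this.

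The subgroup analysis has the same problem in another form. If coaching lowers HbA1c early, some intervention participants just above 58 mmol/mol would be classed as high control while comparable controls would not. Subgroup membership would then depend on allocation, which section 12.8 sets out to prevent.

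**Working it through.** **Does the text allow it?** There are two cases, because the SAP does not define the baseline date or give the interval from baseline to randomisation.
- If the baseline date is the randomisation date, the whole later half of the window is after randomisation.
- If it is an earlier visit, the problem arises whenever randomisation follows within six weeks.

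No section requires a baseline value to precede randomisation or the first session. The word recent in section 12.6 suggests looking back but sets no limit. The laboratory-only analysis in section 12.7.1 does not exclude late values by rule, since the window covers both sources.

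**The plan's own figures (section 9).** Inputs: difference 5.5 mmol/mol, SD 15.3, two-sided 5%, 20% attrition, 10–12 participants per coach, ICC 0.02 in the intervention arm, correlation 0.3, N = 380.
- Analysed per arm: 0.8 × 380 / 2 = 152.
- Adjusted SD: 15.3 × √(1 − 0.3²) = 14.60.
- Design effect at 12 per coach: 1 + 11 × 0.02 = 1.22, intervention arm only.
- SE: 14.60 × √((1 + 1.22)/152) = 1.764.
- Power: Φ(5.5/1.764 − 1.96) = Φ(1.158) = 87.7%. At 10 and 11 per coach it is 88.2% and 88.0%.

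The stated 88% is reproduced. The original calculation (N = 450) gives 89.9–90.4% against the stated 90% or so. No planned figure is wrong on this point.

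**Size of the bias.** If a share f of intervention participants have a baseline already lowered by s, the mean baseline in that arm is too low by f × s. Adjustment with slope β then shrinks the estimated difference by

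bias = β × f × s.

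- β = 0.3: the SAP's baseline to 12-month correlation, taken as a slope by assuming equal SDs.
- f = 10–30%: assumed; the SAP gives no figure.
- s = 1.5–2.75 mmol/mol: assumed; this is 27–50% of the 5.5 target.

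| f | s | bias (mmol/mol) | % of 5.5 | power (12 per coach) |
|---|---|---|---|---|
| – | – | 0 | 0 | 87.7% |
| 10% | 1.5 | 0.3 × 0.10 × 1.5 = 0.045 | 0.8% | 87.1% |
| 30% | 2.75 | 0.3 × 0.30 × 2.75 = 0.25 | 4.5% | 84.6% |

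Power here is Φ((5.5 − bias)/1.764 − 1.96).

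**Size of the subgroup misclassification.** Assume baseline HbA1c is normal with SD 15.3. The share lying within s above the cut is at most s × 0.399/15.3: 3.9% for s = 1.5 and 7.2% for s = 2.75. Multiplied by f, at most 0.10 × 3.9% = 0.4% to 0.30 × 7.2% = 2.2% of the intervention arm would change subgroup.

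**What exclusion without imputation would cost.** If late baselines were set to missing in both arms and those participants left the model, power at 12 per coach would be about 84% with 10% lost (n = 136.8 per arm). With 30% lost (n = 106.4) it would be about 74%, or 76% if coach clusters shrink in proportion. This is a larger loss than the bias causes at the same share.

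**The case against.** The strongest reply is that exposure is narrow. Section 12.6 describes laboratory blood as taken at the visit, so those values should carry the visit date. The late route is therefore realistically medical records, used only when laboratory results are unavailable. To do harm, such a result must be dated after randomisation, follow at least one coaching session and still fall within the window. Section 7.1 speaks only of the follow-up date, so naming baseline in section 12.6 may be loose drafting. An analyst who followed section 12.8 strictly would not use a post-coaching value for the subgroup. The protocol, not shown, may also require baseline blood before randomisation.

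Much of this stands, and it limits the size and frequency of the problem. It does not remove it: section 12.6 is the rule that selects values, it names baseline, and nothing in the SAP protects the covariate as section 12.8's principle might protect the subgroup. If the protocol has such a rule, the SAP should still state it.

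A reader might go further and infer three things that the SAP does not support:
- **That the bias is certain to be toward the null.** This needs a positive slope, an early effect with the same sign as the 12-month effect, and late values otherwise comparable between arms. It is the expected direction, not a guaranteed one.
- **That it could reach about 0.50 mmol/mol (9% of the target).** This needs a slope of 0.6, twice the SAP's correlation: 0.6 × 0.30 × 2.75 = 0.495.
- **That laboratory and record values are equally exposed.** The window covers both, but laboratory sampling is tied to the visit.

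**Conclusion.** The point holds as a defect in a stated rule. As written, section 12.6 admits a post-randomisation HbA1c value as the baseline covariate in the primary model and as the 58 mmol/mol subgroup variable; the latter conflicts with section 12.8. How often this would happen cannot be determined from the SAP. The effect is probably small: about 0.05–0.25 mmol/mol (1–4.5% of 5.5), expected toward the null if the intervention lowers HbA1c early. That range rests on assumed late shares and early changes and on reading the correlation of 0.3 as a slope. The planned sample size and power figures are unaffected. The reason to act is that the rule is avoidable and bears on the primary estimate, not that the number is large.

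**What to change.** In section 12.6, state that a baseline HbA1c value must be dated no earlier than six weeks before the baseline date and no later than the date of randomisation, and define the baseline date. Keep ±6 weeks for months 6 and 12 only. Refer to the same rule in section 12.8 for the diabetes-control subgroup. The look-back should stay anchored on the baseline date: counting it from randomisation could discard valid baseline-visit values when randomisation is delayed.

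Treat later values as missing baseline and impute baseline in the primary analysis, for example with the baseline-imputation approach in section 12.7.2. At present that imputation is a sensitivity analysis, done only if judged appropriate, so without this change the affected participants would drop out of the primary model. State also how participants with an imputed baseline are handled in the subgroup analysis.

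The cost is a few sentences and somewhat more missing baseline values to impute. Section 12.6 already has the test date recorded for medical-record results. It mentions no sample date for laboratory results, so the visit date would serve there or the sample date should be confirmed as available.

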12.7.2 Missing data

The amount of missing data will be reported for each randomised arm, and we will also compare the baseline characteristics of participants who are included in the primary analysis to ensure that any attrition has not produced any imbalance in the groups in important covariates. We will explore the extent and pattern of missing data and, if appropriate, will undertake multiple imputation to assess the impact of missing data on treatment effect estimates.

Multiple Imputation by Chained Equation (MICE) will be used as the method for imputation (10)(11). The imputation model that will be used to impute Hba1c at baseline, 6 months and 12 months. We will present results from the following models:

Baseline imputed only- the imputation model will include HbA1c at baseline and 6 months, age, sex, ethnicity, IMD decile and treatment arm. Thirty multiply imputed data sets will be used. Missing 12-month HbA1c values will be imputed but removed again before analysis (12)

Baseline and 12 months- the same model described above will be used and the imputed 12-month HbA1c values will remain.

Treatment effects and their 95% CIs will be presented in a forest plot alongside those produced using the primary analysis methods and other sensitivity analyses (Ref: Table 7).

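### Section 12.6 gives no rule for a missing baseline HbA1c, so the primary model as written drops participants who have observed follow-up values

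*SAP*

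**What the plan says.** Section 12.6 makes HbA1c at 6 and 12 months the dependent variable, "adjusting for baseline HbA1c scores and outcome source (central lab or medical records"), so baseline HbA1c is a fixed-effect covariate. Values from either source are accepted "providing they are within +/-6 weeks from the date of the specified timepoint (baseline, 6- and 12-months post randomisation"), followed by "Values outside of this window will be counted as missing". The window rule therefore applies to baseline as well as to the two follow-ups.

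On missing data the section says "We will conduct analyses with all observed data. Mixed effects regression models use all available data", and the sentence ends with a missing-at-random assumption for outcomes that were not observed. Section 12.2 adds the principle "Analysis of primary and secondary outcomes will be intention-to-treat (ITT) (unless otherwise stated"). Neither section gives a rule for a participant whose baseline HbA1c is missing.

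Section 12.7.2 plans multiple imputation of HbA1c at all three time points, as a sensitivity analysis and only if judged appropriate. The first of its two models is described as "Baseline imputed only- the imputation model will include HbA1c at baseline and 6 months", plus demographic variables and treatment arm. Imputed 12-month values are taken out again before that analysis. Nothing is said about taking out imputed 6-month values.

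**The concern.** A likelihood-based mixed model keeps a participant who has one of the two outcomes. It cannot keep a participant whose covariate is missing, because that person's rows have no linear predictor. Standard software deletes those rows. Someone with valid HbA1c at both 6 and 12 months but no valid baseline would contribute nothing to the primary estimate.

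The SAP allows for missing baselines, since it plans to impute them and its window rule can create them. The only place where these participants return is a conditional sensitivity analysis. The checks on missingness in 12.6 compare people with and without missing outcomes, so a person with outcomes but no baseline counts there as complete.

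Precision and the match between the stated and actual analysis set are at stake. The revised target of 380 (section 9) relies on the gain from baseline adjustment, and deleting people without a baseline erodes that gain.

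**Working it through.** **1. Does the model drop these people?** A random-intercept model (no coach effect) with baseline as covariate was fitted to simulated data. There were 380 participants with both outcomes observed (760 rows), and baseline was blanked for 38. The fit used 684 rows and 342 participants. All 38 were lost at both visits (76 rows), including 38 observed 12-month values.

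**2. Inputs (SAP sections 9, 10 and 12.2).** Difference 5.5 mmol/mol; SD 15.3; two-sided 5%; attrition 20%; 10 to 12 participants per coach with ICC 0.02, intervention arm only; baseline correlation 0.3; 1:1 allocation; 380 randomised. The share of completers without a valid baseline is not given and is assumed below.

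**3. Reproducing the plan's figures.** With m participants per coach, the design effect is DE = 1 + (m − 1) × 0.02, which is 1.20 at m = 11.

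Original size, no baseline adjustment:
- n per arm = (1.960 + 1.282)² × 15.3² × (1.20 + 1) / 5.5² ≈ 179
- 179 / 0.8 rounds up to 224 per arm, or 448 in total (446 at m = 10, 454 at m = 12), against 450 stated.

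Revised size:
- n per arm = 190 × 0.8 = 152, or 304 completers
- variance of the difference = 15.3² × (1 − 0.3²) × 2.20 / 152 = 3.083, so SE = 1.756
- power = Φ(5.5 / 1.756 − 1.960) = Φ(1.172) = 0.880 (0.882 at m = 10, 0.877 at m = 12), against 88% stated.

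Both reproduce.

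**4. Dropping completers without a valid baseline.** Replace 152 by 152 × (1 − f), where f is the assumed share. At f = 10%, n = 136.8, variance = 3.426, SE = 1.851 and power = Φ(1.012) = 0.844.

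| Assumed share f | Completers analysed | Power, m = 12 to m = 10 |
|---|---|---|
| 0 | 304 | 0.877–0.882 |
| 2% | 298 | 0.870–0.876 |
| 5% | 289 | 0.860–0.866 |
| 10% | 274 | 0.841–0.847 |
| 15% | 258 | 0.820–0.827 |

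**5. Break-even with no adjustment.** At correlation 0.3, adjustment multiplies the variance by 1 − 0.09 = 0.91. Losing 9% of completers multiplies n by 0.91, which cancels the gain exactly. An unadjusted comparison of all 304 has power 0.845–0.851, against 0.841–0.847 for the adjusted one with 10% dropped.

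**6. The baseline-only imputation model.** Section 12.6 makes both 6- and 12-month HbA1c dependent variables. Section 12.7.2 imputes both but removes only the 12-month imputations. Read literally, imputed 6-month outcomes stay in an analysis described as imputing baseline alone.

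**The case against.** The statement about available data goes on to refer to missing outcomes, and for outcomes it is right. Section 12.7.2 speaks of the participants included in the primary analysis, so the SAP does not claim that everybody enters the model. Section 12.2 does not define intention-to-treat. A reader might infer that the SAP makes a false claim or openly adopts a complete-baseline primary analysis. The text does not support that: the exclusion is implied by the model form and default deletion. What stands is that 12.6 has no rule and that the model, fitted as written, does not do what the section intends.

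The issue is also partly anticipated. The baseline-only imputation model would restore these participants, with 30 imputations and a row in Table 7 beside the primary result. This mitigates the problem, but the analysis is conditional and leaves the primary estimate unchanged.

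The power figures may overstate the loss. A baseline can come from medical records when blood is refused, so the share may be near zero. People without a baseline may also be those without a 12-month value, which would reduce the extra loss below that shown. The 380 is a minimum, and section 12.6 calls the single-time-point calculation conservative. All of this stands, so the table shows a range and predicts nothing.

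Two further inferences are tempting. One is that the treatment estimate is biased. A baseline taken before randomisation cannot depend on allocation, so dropping people without one costs precision and narrows the analysis set without clear bias. The other is that the loss falls on people reluctant to give blood, as a group the trial particularly wants to represent. The SAP offers such people the records route, which can also supply a baseline, and nowhere states that aim.

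**Conclusion.** The point holds as a gap in the primary analysis with a better method readily available. Its size depends wholly on a share that the SAP does not report: about 1 point of power at 2% missing, 2 at 5%, 4 at 10% and 6 at 15%, from a start of about 88%. These figures assume that missing baselines are unrelated to 12-month attrition and use the SAP's own planning values. With few missing baselines the practical effect is negligible, though the rule should still be fixed in advance. The 6-month imputation point is a smaller drafting defect in a sensitivity analysis.

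**What to change.** In section 12.6, state that the primary analysis includes every randomised participant with at least one valid follow-up HbA1c, and specify one of these:

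- Fill a missing baseline with the mean pooled over both arms, without reference to allocation, and add a missing-baseline indicator to the model.
- Put baseline in the outcome vector with the arm means constrained equal at baseline.

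With either, restrict the baseline value to measurements taken before randomisation. The window around the baseline date may admit later values, and the pooled fill and the equal-means constraint are safe only for a pre-randomisation measure. The restriction may itself make a few more baselines missing, which the rule then handles.

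Keep the complete-baseline analysis as a sensitivity analysis, and report by arm how many participants have follow-up HbA1c but no valid baseline.

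In section 12.7.2, remove imputed 6-month as well as imputed 12-month outcomes from the baseline-only imputation analysis.

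The cost is a few sentences, entered in the section 13 amendment log, and one derived baseline variable with its indicator. No new data are needed.
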